# **3. STUDY OBJECTIVES**

# **3.1. Primary Objectives**

## Part A:

- To evaluate the safety and tolerability of the VRC-FLUMOS0111-00-VP vaccine, administered as a single dose at 20 mcg IM via needle and syringe to healthy adults.
- To evaluate the safety and tolerability of the VRC-FLUMOS0111-00-VP vaccine, administered as a single dose at 60 mcg IM via needle and syringe to healthy adults.

## Part B:

- To evaluate the safety and tolerability of the VRC-FLUMOS0111-00-VP vaccine, administered alone as a single dose at 100 mcg IM via needle and syringe to healthy adults.
- To evaluate the safety and tolerability of the VRC-FLUMOS0111-00-VP vaccine, administered as a single dose at 100 mcg with Adjuplex at 20% v/v IM via needle and syringe to healthy adults.
- If enrolled, to evaluate the safety and tolerability of the VRC-FLUMOS0111-00-VP vaccine, administered as a single dose at 60 mcg with Adjuplex at 20% v/v IM via needle and syringe to healthy adults.

## **Part C** (if enrolled):

- To evaluate the safety and tolerability of the VRC-FLUMOS0111-00-VP vaccine, administered alone as a single dose at TBD mcg IM via needle and syringe to healthy adults.
- To evaluate the safety and tolerability of the VRC-FLUMOS0111-00-VP vaccine, administered as a single dose at TBD mcg with Adjuplex at 20% v/v IM via needle and syringe to healthy adults.

# **3.2.** Secondary Objectives

## Part A:

- To evaluate antibody responses to the VRC-FLUMOS0111-00-VP vaccine administered as a single dose at 20 or 60 mcg IM via needle and syringe at two weeks after injection.
- To evaluate antibody responses between VRC-FLUMOS0111-00-VP administered as a single dose at 60 mcg IM via needle and syringe and Flucelvax® licensed vaccine at two weeks after vaccination.

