## PRÉCIS

- Title:VRC 325: A Phase I Open-Label Clinical Trial To Evaluate the Dose, Safety, Tolerability and
Immunogenicity of Mosaic Quadrivalent Influenza Vaccine with and without Adjuplex Compared with a
Licensed Inactivated Seasonal QIV, in Healthy Adults.
- **Design:** This is a Phase I, open-label, dose escalation study to evaluate the dose, safety, tolerability, and immunogenicity of the mosaic quadrivalent influenza vaccine VRC-FLUMOS0111-00-VP (FluMos-v1). The hypotheses are that the FluMos-v1 vaccine is safe and tolerable and will elicit an immune response. The primary objective is to evaluate the safety and tolerability of the investigational vaccine alone or with adjuvant in healthy adults. Secondary objectives relate to immunogenicity of the investigational vaccine and dosing regimen compared with the licensed inactivated seasonal Flucelvax® quadrivalent influenza vaccine (QIV) in healthy adults.

StudyThe investigational vaccine FluMos-v1 was developed by the Vaccine Research Center (VRC), NationalProducts:Institute of Allergy and Infectious Diseases (NIAID) and is composed of the following 4 influenza strains:
Influenza A (H1: A/Idaho/07/2018 and H3: A/Perth/1008/2019) and Influenza B (Victoria lineage:
B/Colorado/06/2017 and Yamagata lineage: B/Phuket/3073/2013. FluMos-v1 is supplied in a single-use
vial at a concentration of 180 mcg/mL.

In Part A, FluMos-v1 was compared to licensed 2020-2021 QIV Flucelvax® developed by Seqirus, Inc. and composed of the following 4 influenza strains: Influenza A (H1: A/Hawaii/70/2019 (H1N1) pdm09-like virus and H3: A/Hong Kong/45/2019 (H3N2)-like virus) and Influenza B: Victoria lineage: B/Washington/02/2019-like virus and Yamagata lineage: B/Phuket/3073/2013-like virus).

In Part B, a higher dose of FluMos-v1 was tested that more closely matches the amount of each HA antigen in Flucelvax. The adjuvant Adjuplex® was added to FluMos-v1 to evaluate the potential for increased immunogenicity. All study enrollments and injections have been completed, and no further enrollments are planned in this study.

Adjuplex is provided as a sterile, pyrogen-free, homogeneous solution filled to 0.7 mL in 3-mL glass vials. Adjuplex is mixed with study products in the pharmacy during preparation prior to vaccination at a 20% dose by volume.

FluMos-v1, FluMos-V1 plus Adjuplex, and Flucelvax® are administered intramuscularly (IM) in the deltoid muscle via needle and syringe.

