## 1.6.2. FluMos-v1 Vaccine

VRC 316, VRC 321 and VRC 323 studies showed that two dose levels of the ferritin nanoparticle-based vaccines, 20 mcg and 60 mcg of HA-F A/Sing, of H1ssF\_3928 and of H10ssF-6473 respectively, were safe and well tolerated. The same vaccine doses were also evaluated in preclinical evaluations of FluMos-v1 vaccine as discussed in Section 2.4.

In pre-clinical studies, addition of adjuvant increased the immunogenicity of FluMos-v1.

In study VRC 325 Part A, FluMos-v1 vaccine was evaluated at 20 mcg and 60 mcg as a single dose. The dose levels chosen to be tested clinically were selected based on the preclinical immunogenicity studies. Both the 20 mcg and 60 mcg doses were safe and well tolerated as described in Section 1.5.1. Immunogenicity analysis of Part A is still ongoing, but preliminary

data indicate the need to increase the dose and/or add an adjuvant to improve immunogenicity. Given the safety profile of 60 mcg, and toxicology studies supporting doses of up to 190 mcg, in Part B, the VRC will test a single dose of 100 mcg with and without adjuvant, with optional Part C to test a single dose up to 190 mcg, after IRB approval. An initial dose of 100 mcg was chosen for Part B because it has an HA protein content of approximately 62 mcg, which more closely matches the HA content of Flucelvax (60 mcg of HA).

Since the nanoparticle itself makes up close to 40% of the total weight, our initial dose of 60 mcg was not equivalent to the QIV dose per the HA quantity. Therefore, the original 60 mcg dose is not an ideal comparison to the licensed QIV. The 100 mcg dose (Group 4) was included to evaluate the safety of a higher dose of FluMosv-1 on its own before the addition of adjuvant. If we observe adverse safety signals with the 100 mcg dose alone or with Adjuplex, we will stop administering this dose as described in the protocol Section 4.7, and may enroll the 60 mcg plus Adjuplex group, which is built into the protocol as an optional group for additional safety and immunogenicity assessments.

Influenza H1, H3, HBv, and Hby HA strains were selected for evaluation based on the influenza lineage types included in the licensed 2019-2020 seasonal QIV vaccine.

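### The title sets FluMos-v1, with and without Adjuplex, against a licensed QIV, but the only planned Flucelvax contrast is 60 mcg unadjuvanted; the 100 mcg groups have none

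*Combined protocol and SAP*

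**What the plan says.** - **Title (Précis):** "Mosaic Quadrivalent Influenza Vaccine with and without Adjuplex Compared with a" licensed seasonal QIV.
- **Design sentence (Précis):** "Secondary objectives relate to immunogenicity of the investigational vaccine and dosing regimen compared with the licensed inactivated seasonal Flucelvax® quadrivalent influenza vaccine (QIV"). It limits neither the dose nor the Part, and it does not mention Adjuplex.
- **Study Products (Précis):** "In Part A, FluMos-v1 was compared to licensed 2020-2021 QIV Flucelvax". For Part B it says only that "a higher dose of FluMos-v1 was tested that more closely matches the amount of each HA antigen in Flucelvax".
- **Section 1.6.2:** "the original 60 mcg dose is not an ideal comparison to the licensed QIV", because "the nanoparticle itself makes up close to 40% of the total weight". The 100 mcg dose was picked because "it has an HA protein content of approximately 62 mcg, which more closely matches the HA content of Flucelvax (60 mcg of HA"). The same section also cites preliminary Part A immunogenicity and the safety of 60 mcg, and gives Group 4's purpose as checking the safety of the higher dose before adjuvant is added.
- **Section 3.2, Part A (Week 2):** "To evaluate antibody responses between VRC-FLUMOS0111-00-VP administered as a single dose at 60 mcg IM via needle and syringe and Flucelvax® licensed vaccine". Part B evaluates each 100 mcg group by itself and compares 100 mcg alone with 100 mcg plus Adjuplex. Flucelvax does not appear there.
- **Section 6.3.2:** names Flucelvax in the Part A endpoint but not in the Part B and C endpoint.
- **Section 6.3.6:** sizes comparisons only within a Part (15 versus 15, 13 versus 13).
- **Section 6.4.4:** gives exact intervals for response rates and summaries of distributions. It specifies no between-group estimate for any contrast.

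**The concern.** A reader of the title expects to learn how FluMos-v1, plain and adjuvanted, performs against a licensed QIV. The objectives deliver this only for the plain vaccine, at a dose whose HA content the protocol itself regards as poorly matched. The dose described as the closer match, and the adjuvanted vaccine, have no planned estimate against Flucelvax.

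Groups 3, 4 and 5 can still be summarised: Section 6.4.4 allows summaries, and Section 6.4.6 allows reports by study group. Side by side, those summaries would invite the missing comparison with no interval and no caveat. Nothing in the plan tells the reader that the groups were not randomised, or that the two Parts were enrolled in different years after different vaccine seasons.

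**Working it through.** **1. The plan's own power figures.** Section 6.3.6 gives detectable effect sizes of 1.06 (1.23) SD for 15 per arm and 1.15 (1.33) SD for 13 per arm, at 80% (90%) power. A two-sample t-test at two-sided 0.05 (the alpha is not stated, so it is assumed) gives 1.060 (1.226) and 1.145 (1.326). They reproduce. The gap lies in the objectives and the analysis, not in this arithmetic.

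**2. HA content.** Section 1.6.2 puts the scaffold at close to 40% of the weight, and puts 100 mcg at about 62 mcg HA. The HA fraction is therefore 0.60 to 0.62.
- 60 mcg dose: 60 × 0.60 = 36.0 mcg and 60 × 0.62 = 37.2 mcg. Shortfall against 60 mcg: 1 − 36.0/60 = 40% and 1 − 37.2/60 = 38%.
- 100 mcg dose: 60 to 62 mcg, a ratio of 1.00 to 1.03 to Flucelvax.

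**3. Which contrasts are planned.**

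| Contrast at Week 2 | Planned in 3.2? | Sized in 6.3.6? |
|---|---|---|
| Group 2 (60 mcg) vs Group 3 (Flucelvax) | Yes | Yes, 15 vs 15 |
| Group 4 (100 mcg) vs Group 5 (100 mcg + Adjuplex) | Yes | Yes, 13 vs 13 |
| Group 4 vs Group 3 | No | No |
| Group 5 vs Group 3 | No | No |

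**4. Precision of the missing contrasts.** The unadjusted 95% CI half-width in SD units is t(0.975, df) × √(1/n₁ + 1/n₂).
- 13 vs 15: 0.779. Planned 15 vs 15: 0.748. Planned 13 vs 13: 0.810.
- With Day 0 adjustment (df 25), multiply by √(1 − ρ²). At an assumed ρ of 0.3 to 0.7 this gives 0.744 to 0.557.
- At an assumed log10 titre SD of 0.3 to 0.6, the adjusted ratio has a CI factor from 10^(0.557 × 0.3) = 1.47 to 10^(0.744 × 0.6) = 2.80 either side (unadjusted 1.71 to 2.93).

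Sampling error is thus close to that of the planned contrasts. Comparability is the weaker side.

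**5. Comparability across Parts.**
- *Calendar (1.5.1).* Part A enrolled 24 May to 17 August 2021, and Part B 6 September 2022 to 20 April 2023. The shortest gap (17 August 2021 to 6 September 2022) is 385 days; the longest (24 May 2021 to 20 April 2023) is 696 days.
- *Prior vaccination (4.2.1, 4.2.2, schema footnotes).* The eligible seasons differ, and the B suffix refers to 2020-2021 in Part A but to 2021-2022 or 2022-2023 in Part B.
- *Strains (2.1, 2.2).* H1, H3 and B/Victoria differ between the two vaccines; only the B/Yamagata component shares a strain name. A ratio therefore depends on which vaccine's HA is the assay antigen. This applies to the planned 60 mcg contrast too.
- *Assay runs.* The documents do not say whether the Parts were tested together. Suppose they were not, and one Part carried an additive log10 shift d at both Day 0 and Week 2. Day 0 adjustment leaves d × (1 − ρ) when the two SDs are equal. For assumed d of 0.1 to 0.3 and ρ of 0.3 to 0.7 the residual is 0.03 to 0.21 log10, a factor of 1.07 to 1.62. A log fold-rise contrast leaves d − d = 0. Its cost is precision: its SD is √(2(1 − ρ)) times the titre SD, so the half-width is 0.779 × 1.183 = 0.92 SD at ρ = 0.3 and 0.779 × 0.775 = 0.60 SD at ρ = 0.7.

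**6. Status.** The last injection on 20 April 2023 plus 280 days is 25 January 2024, which is 383 days before the 11 February 2025 version date. Section 1.6.2 also shows that preliminary Part A immunogenicity was known before Part B. Any contrast added now is post hoc.

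**The case against.** The best defence is that the plan is consistent below the title. The Précis ties the Flucelvax comparison to Part A, and Sections 3.2, 6.3.2 and 6.3.6 follow that split. Part B enrolled no Flucelvax group, so leaving out a cross-Part contrast is a defensible choice in a Phase I safety trial. This largely stands. It reduces the point to a mismatch of scope plus an inexpensive improvement.

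Four stronger readings are tempting, and the documents do not support them.
- *The Design sentence also promises an adjuvanted comparison with the QIV.* It does not mention Adjuplex; only the title does.
- *The 100 mcg dose was chosen for a Flucelvax contrast that was then dropped.* HA match is one reason among several in Section 1.6.2, and no passage promises that contrast.
- *Only Groups 4 and 5 lack an estimate with an interval.* Section 6.4.4 specifies no ratio for the planned 60 mcg contrast either.
- *The planned contrasts are randomised and the cross-Part ones are not.* The documents describe no randomisation. Group assignment is known before enrolment (4.4.6), Group 3 could enrol at any time (4.1), and with Groups 4 and 5 both open, subjects were placed at the investigator's discretion (4.5).

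A reader might also take the factor of 1.07 to 1.62 as a bias in this trial. It is not: every input is assumed, and it arises only if sera are neither co-tested nor bridged.

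Section 3.3 could be said to fill the gap, since an exploratory objective names both vaccines. It gives no dose, group or contrast, so it does not.

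**Conclusion.** The point holds as a mismatch of scope. The title covers FluMos-v1 with and without Adjuplex against a licensed QIV, and the Design sentence covers the vaccine and regimen without a dose limit. The plan has one Flucelvax contrast, unadjuvanted, at a dose carrying 38 to 40% less HA than Flucelvax by the protocol's own figures. Groups 4 and 5 have none.

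The HA figures rest on Section 1.6.2 alone. The 0.78 SD half-width needs only the group sizes. The adjusted widths and ratio factors rest on assumed correlations and titre SDs, shown as ranges. The primary safety objectives are untouched. The cross-Part contrasts can support interpretation but cannot settle how either 100 mcg group compares with the QIV.

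**What to change.** 1. In 6.4.4, report the planned 60 mcg versus Flucelvax Week 2 contrast as a geometric mean ratio with a 95% CI, adjusted for Day 0 titre.
2. Add Group 4 versus Group 3 and Group 5 versus Group 3 in the same form as exploratory, descriptive, post hoc contrasts without hypothesis tests. Place them under 3.3 and 6.4.4 or in a report addendum, not in 3.2. Compute them only if Day 0 and Week 2 sera from both Parts were co-tested or bridged on the same platform; otherwise give by-group summaries only.
3. For each ratio, name the assay antigen and say whether it matches FluMos-v1, Flucelvax or both. Add a log fold-rise contrast as a sensitivity check.
4. State that every between-group contrast is non-randomised; that the cross-Part ones are also non-concurrent (May to August 2021 versus September 2022 to April 2023), with different prior-vaccination seasons; and that Group 5 also adds adjuvant.
5. If the contrasts in item 2 are not added, limit the title and Design sentence to the 60 mcg Part A comparison.

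**Cost.** Item 5 is wording only. Items 1 to 4 need no new participants or visits, because Appendix I already schedules Day 0 and Week 2 serum in both Parts. If the Parts were assayed separately, item 2 needs a bridging panel or re-testing of stored sera. The downside is that the cross-Part estimates are imprecise and supportive only.

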## Part B:

• To evaluate antibody responses to the VRC-FLUMOS0111-00-VP vaccine administered alone as a single dose at 100 mcg IM via needle and syringe at two weeks after injection.

- To evaluate antibody responses to the VRC-FLUMOS0111-00-VP vaccine administered as a single dose at 100 mcg with 20% v/v of Adjuplex IM via needle and syringe at two weeks after injection.
- To evaluate antibody responses between 100 mcg of VRC-FLUMOS0111-00-VP alone and 100 mcg of VRC-FLUMOS0111-00-VP with 20%v/v of Adjuplex IM via needle and syringe at two weeks after vaccination.
- If Group 6A-6B is enrolled, evaluate antibody responses to the VRC-FLUMOS0111-00-VP vaccine administered as a single dose at 60 mcg with 20% v/v of Adjuplex IM via needle and syringe at two weeks after injection.

## **Part C** (if enrolled):

- To evaluate antibody responses to the VRC-FLUMOS0111-00-VP vaccine administered alone as a single dose at TBD mcg IM via needle and syringe at two weeks after injection.
- To evaluate antibody responses to the VRC-FLUMOS0111-00-VP vaccine administered as a single dose at TBD mcg with 20% v/v of Adjuplex IM via needle and syringe at two weeks after injection.
- To evaluate antibody responses between TBD mcg of VRC-FLUMOS0111-00-VP alone and TBD mcg of VRC-FLUMOS0111-00-VP with 20%v/v of Adjuplex IM via needle and syringe at two weeks after vaccination.

# **3.3.** Exploratory Objectives

- To evaluate the specificity and functionality of VRC-FLUMOS0111-00-VP and Flucelvax® vaccine-induced antibodies and the immune response at various timepoints throughout the study.
- To evaluate the frequency, magnitude, phenotype, and specificity of HA-specific B-cell, T-cell, and antibody responses at various time points throughout the study.
- To evaluate the antibody response to the pentameric scaffold lumazine synthase and engineered trimer at various time points throughout the study.

# 4. STUDY DESIGN, SUBJECT POPULATION AND CLINICAL PROCEDURES

# 4.1. Study Design

This is a Phase I, open-label, dose escalation study to evaluate the dose, safety, tolerability, and immunogenicity of the FluMos-v1 vaccine with or without Adjuplex in healthy adults. The study schema is shown in **Table 1**. The hypotheses are that the vaccine with or without Adjuplex is safe, tolerable, and will induce an antibody response to the four influenza strains: H1, H3, HBv, and Hby. The study will be conducted by the VRC Clinical Trials Program at a single site (Vaccine Evaluation Clinic, VEC) at the NIH Clinical Center (NIH CC), Bethesda, MD.

VRC 325 Vaccination Schema					
Group	Subjects	Day 0	Product		
	Part A				
1A 1B 	- 5	20 mcg	FluMos-v1		
2A 2B 	- 15	60 mcg	FluMos-v1		
3A 3B 	- 15	60 mcg	Flucelvax®		
		Part B			
4A 4B 	- 13	100 mcg	FluMos-v1		
5A 5B 	- 13	100 mcg	FluMos-v1 + Adjuplex (20% v/v)		
6A 6B 	- 13	 60 mcg	FluMos-v1 + Adjuplex (20% v/v)		
		 Part C			
7A 7B 	- 13	 X mcg	FluMos-v1		
8A 8B 	- 13	 X mcg	FluMos-v1 + Adjuplex (20% v/v)		
Total	100 4	
 
Includes subjects who received the 2020-2021 seasonal influenza vaccine.
 
Includes subjects who received the 2021-2022 or 2022-2023 seasonal influenza vaccine.
 
Group 6 and Part C of the study are optional, and the decision was made not to enroll groups 6-8.
 
Study enrollment has been completed with 35 subjects enrolled in Part A (Groups 1-3) and 26 in Part B (Groups 4-5) of the study.
 
			

## Table 1: Study Schema

In Part A and Part B, the study had staged enrollment with required interim safety reviews, as described in Section 4.5, Criteria for Dose Escalation.

Subjects enrolled in Group 3A-3B enrolled at any time after the study was open to accrual as they received only a licensed influenza vaccine.

The optional Group 6 and Part C of the study (Groups 7-8) were not enrolled in the study.

# 4.2. Study Population

All inclusion and exclusion criteria must be evaluated for eligibility.

## 4.2.1. Inclusion Criteria

## A subject must meet all of the following criteria:

- 1. Healthy adults between the ages of 18-50 years inclusive
- 2. Based on history and physical examination, in good general health and without history of any of the conditions listed in the exclusion criteria
- 3. Part A: Received at least one licensed influenza vaccine from 2016 through the 2019-2020 influenza season
- 4. **Part B** and C: Received at least one licensed influenza vaccine from 2017 through the 2022-2023 influenza season
- 5. Able and willing to complete the informed consent process
- 6. Available for clinic visits for 40 weeks after enrollment and through an influenza season
- 7. Able to provide proof of identity to the satisfaction of the study clinician completing the enrollment process
- 8. Physical examination and laboratory results without clinically significant findings and a Body Mass Index (BMI) ≤ 35 within the 56 days before enrollment

## Laboratory Criteria within 56 days before enrollment:

- 9. White blood cells (WBC) and differential within institutional normal range or accompanied by the site Principal Investigator (PI) or designee approval
- 10. Total lymphocyte count  $\geq 800$  cells/ $\mu$ L
- 11. Platelets = 125,000 500,000 cells/µL
- 12. Hemoglobin within institutional normal range or accompanied by the PI or designee approval
- 13. Alanine aminotransferase (ALT)  $\leq$  1.25 x institutional upper limit of normal (ULN)
- 14. Aspartate aminotransferase (AST)  $\leq$  1.25 x institutional ULN
- 15. Alkaline phosphatase (ALP) <1.1 x institutional ULN
- 16. Total bilirubin within institutional normal range or accompanied by the PI or designee approval.
- 17. Serum creatinine  $\leq 1.1$  x institutional ULN
- 18. Negative for HIV infection by an FDA-approved method of detection

## Criteria applicable to women of childbearing potential:

19. Negative beta-human chorionic gonadotropin ( $\beta$ -HCG) pregnancy test (urine or serum) on the day of enrollment

20. Agrees to use an effective means of birth control from at least 21 days prior to enrollment through the end of the study

## 4.2.2. Exclusion Criteria

A participant will be excluded if one or more of the following conditions apply:

1. Women breast-feeding or planning to become pregnant during the study

Participant has received any of the following substances:

- 2. More than 10 days of systemic immunosuppressive medications or cytotoxic medications within the 4 weeks prior to enrollment or any within the 14 days prior to enrollment
- 3. Blood products within 16 weeks prior to enrollment
- 4. Live attenuated vaccines within 4 weeks prior to enrollment
- 5. Inactivated vaccines within 2 weeks prior to enrollment
- 6. Investigational research agents within 4 weeks prior to enrollment or planning to receive investigational products while on the study
- 7. Current allergy treatment with allergen immunotherapy with antigen injections, unless on maintenance schedule
- 8. Current anti-TB prophylaxis or therapy
- 9. Previous investigational H1, H2, or H10 influenza vaccines, including Part A participants
- 10. **Part A**:
  - a. Groups 1A, 2A, and 3A only: Receipt of the 2020-2021 season's licensed influenza vaccine at any time prior to enrollment
  - b. Groups 1B, 2B, and 3B only: Receipt of the 2020-2021 season's licensed influenza vaccine within 4 months prior to enrollment.
- 11. Part B and C:
  - a. Groups 4A, 5A, 6A, 7A, and 8A only: Receipt of the 2021-2022 or 2022-2023 season's licensed influenza vaccine at any time prior to enrollment
  - b. Groups 4B, 5B, 6B, 7B, and 8B only: Receipt of the 2021-2022 or 2022-2023 season's licensed influenza vaccine within 4 months prior to enrollment.

Subject has a history of any of the following clinically significant conditions:

- 12. Serious reactions to vaccines that preclude receipt of the study vaccination as determined by the investigator
- 13. Hereditary angioedema, acquired angioedema, or idiopathic forms of angioedema
- 14. Asthma that is not well controlled
- 15. Diabetes mellitus (type I or II), with the exception of gestational diabetes
- 16. Thyroid disease that is not well controlled
- 17. Idiopathic urticaria within the past year
- 18. Autoimmune disease or immunodeficiency

- 19. Hypertension that is not well controlled
- 20. Bleeding disorder diagnosed by a doctor (e.g. factor deficiency, coagulopathy, or platelet disorder requiring special precautions) or significant bruising or bleeding difficulties with IM injections or blood draws
- 21. Malignancy that is active or history of malignancy that is likely to recur during the period of the study
- 22. Seizure disorder other than 1) febrile seizures, 2) seizures secondary to alcohol withdrawal more than 3 years ago, or 3) seizures that have not required treatment within the last 3 years
- 23. Asplenia, functional asplenia or any condition resulting in the absence or removal of the spleen
- 24. Guillain-Barré Syndrome
- 25. Any medical, psychiatric, social condition, occupational reason or other responsibility that, in the judgment of the investigator, is a contraindication to protocol participation or impairs a subject's ability to give informed consent.

